4) Subjects with abnormal laboratory tests results, vital signs results, or electrocardiogram (ECG) findings, unless, based on the investigator’s judgment, the findings are not medically significant and would not impact the safety of the subject or the interpretation of the trial results. The medical monitor should be contacted to discuss individual cases, as needed.

In addition, subjects with the following laboratory test and ECG results at screening must be excluded from the trial:

- Platelets $\leq 75000/\text{mm}^3$
- Hemoglobin $\leq 9 \text{ g/dL}$
- Neutrophils, absolute $\leq 1000/\text{mm}^3$
- Aspartate aminotransferase (AST) $> 2 \times$ the upper limit of normal (ULN)
- Alanine aminotransferase (ALT) $> 2 \times$ ULN
- Creatine phosphokinase (CPK) $> 3 \times$ ULN, unless discussed with and approved by the medical monitor
- Creatinine $\geq 2 \text{ mg/dL}$
- QT interval corrected for heart rate using Fridericia’s formula (QTcF) $\geq 450 \text{ msec}$ in men and $\geq 470 \text{ msec}$ in women, unless due to ventricular pacing.

Tests with exclusionary results should be repeated to ensure reproducibility of the abnormality before excluding a subject based on the criteria noted above. For ECGs, perform 3 consecutive recordings. If 2 of the 3 remain exclusionary then the subject must be excluded.

- 5) Subjects with a positive drug screen for cocaine or other illicit drugs are excluded and may not be retested or rescreened. Subjects with a positive urine drug screen resulting from use of cannabis, or prescription or over-the counter medications, or products that, in the investigator's documented opinion, do not signal a clinical condition that would impact the safety of the subject or interpretation of the trial results may continue evaluation for the trial following consultation and approval by the medical monitor. Subjects with positive results for alcohol use will require consultation and approval by the medical monitor in order to verify use does not indicate a substance-use disorder.

Other

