3.1 Study Design

This is a 12-week, multicenter, open-label trial designed to evaluate the safety and tolerability of brexpiprazole treatment in adult subjects diagnosed with BPD. Subjects will receive 2 to 3 mg/day brexpiprazole.

Enrollment into the trial will be drawn from eligible subjects who completed the last treatment visit of the previous double-blind brexpiprazole BPD trials (and took the investigational medicinal product [IMP] through the last scheduled treatment visit) and, in the investigator's judgment, could potentially benefit from treatment with brexpiprazole for BPD.

The trial will be organized as follows:

[figure not shown]
Screening/Baseline: Subjects will be screened for eligibility at the last scheduled treatment visit of the previous double-blind trial. Subjects will sign a separate informed consent form (ICF) at the last scheduled treatment visit of the previous double-blind trial for participation in this trial before any procedures specific to the open-label trial are performed. The assessments from the last scheduled treatment visit of the previous double-blind trial will serve as the baseline measures for this trial for any assessment that is not new (unique) to the open-label trial. Medical history will be updated, if necessary. Informed consent cannot be obtained after the last scheduled treatment visit of the previous double-blind trial without all screening/baseline assessments being repeated. If a subject is unable to rollover immediately, up to 3 days may be permitted between the end of the double-blind trial and the start of IMP in the open-label extension trial; however, this must be discussed with the medical monitor (Note: assessments from the last scheduled treatment visit in the previous double-blind trial that are going to be used as the baseline measures for Trial 331-201-00195 will not need to be repeated if the subject enters Trial 331-201-00195 within 3 days).

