7.1 Baseline Definition

Baseline is defined as the last available measurement prior to the first dose of open-label IMP in the open-label treatment phase.

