9.2 Clinical Laboratory Tests

Summary statistics for mean and mean change from baseline in the routine clinical laboratory measurements, prolactin concentrations, coagulation parameters (PT, aPTT, and INR), HbA1c, and TSH will be provided by parent study treatment group and by visit.

Potentially clinically relevant laboratory measurement test results in the open-label treatment period will be identified for the Safety Sample and will be summarized by parent study treatment group and listed. Criteria for identifying laboratory values of potential clinical relevance are provided in [Appendix 2](#).

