Appendix 1 Criteria for Identifying Vital Signs of Potential Clinical Relevance

Variable	Criterion Value ^a	Change Relative to Baseline ^a
Heart Rate ^b	> 120 bpm < 50 bpm	≥ 15 bpm increase ≥ 15 bpm decrease
Systolic Blood Pressure ^b	> 180 mmHg < 90 mmHg	≥ 20 mmHg increase ≥ 20 mmHg decrease
Diastolic Blood Pressure ^b	> 105 mmHg < 50 mmHg	≥ 15 mmHg increase ≥ 15 mmHg decrease
Orthostatic Hypotension	≥ 20 mmHg decrease in systolic blood pressure and a ≥ 25 bpm increase in heart rate from supine to sitting/standing	Not Applicable (baseline status not considered)
Weight	-	≥ 7% increase ≥ 7% decrease

^a In order to be identified as potentially clinically relevant, an on-treatment value must meet the “Criterion Value” and also represent a change from the subject’s baseline value of at least the magnitude shown in the “Change Relative to Baseline” column.

^b As defined in “Supplementary Suggestions for Preparing an Integrated Summary of Safety Information in an Original NDA Submission and for Organizing Information in Periodic Safety Updates,” FDA Division of Neuropharmacological Drug Products draft (2/27/87).

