Appendix 2 Criteria for Identifying Laboratory Values of Potential Clinical Relevance

Laboratory Tests		Criteria
Chemistry		
AST (SGOT)		$\geq 3 \times$ upper limit of normal (ULN)
ALT (SGPT)		$\geq 3 \times$ ULN
Alkaline phosphatase		$\geq 3 \times$ ULN
Lactate dehydrogenase (LDH)		$\geq 3 \times$ ULN
Blood urea nitrogen (BUN)		≥ 30 mg/dL
Creatinine		≥ 2.0 mg/dL
Uric Acid		
Men		≥ 10.5 mg/dL
Women		≥ 8.5 mg/dL
Bilirubin (total)		≥ 2.0 mg/dL
Creatine phosphokinase (CPK)		$\geq 3 \times$ ULN
Prolactin		$>$ ULN
Hematology		
Hematocrit		
Men		$\leq 37\%$ and decrease of ≥ 3 percentage points from Baseline
Women		$\leq 32\%$ and decrease of ≥ 3 percentage points from Baseline
Hemoglobin		
Men		≤ 11.5 g/dL
Women		≤ 9.5 g/dL
White blood count		$\leq 2,800/\text{mm}^3$ or $\geq 16,000/\text{mm}^3$
Eosinophils		$\geq 10\%$
Neutrophils		$\leq 15\%$
Absolute neutrophil count		$\leq 1,500/\text{mm}^3$
Platelet count		$\leq 75,000/\text{mm}^3$ or $\geq 700,000/\text{mm}^3$
Urinalysis		
Protein		Increase of ≥ 2 units
Glucose		Increase of ≥ 2 units
Casts		Increase of ≥ 2 units
Additional Criteria		
Chloride		≤ 90 mEq/L or ≥ 118 mEq/L
Potassium		≤ 2.5 mEq/L or ≥ 6.5 mEq/L
Sodium		≤ 126 mEq/L or ≥ 156 mEq/L
Calcium		≤ 8.2 mg/dL or ≥ 12 mg/dL
Glucose		
Fasting		≥ 100 mg/dL
Non-Fasting		≥ 200 mg/dL
Total Cholesterol, Fasting		≥ 240 mg/dL
LDL Cholesterol, Fasting		≥ 160 mg/dL
HDL Cholesterol, Fasting		
Men		< 40 mg/dL
Women		< 50 mg/dL
Triglycerides, Fasting		≥ 150 mg/dL

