- CT-8.8.2 Listing of Serious TEAEs or Deaths that Are Related or Probably Related to COVID-19 (Safety Sample)
- CT-8.9 Incidence of Treatment-Emergent Adverse Events of Special Interests (AESIs) by System Organ Class and MedDRA Preferred Term (Safety Sample)
- CT-9.1 Listing of Deaths
- CT-9.2 Listing of Serious Adverse Events
- CT-9.3 Listing of Discontinuations Due to Adverse Events
- CT-10.1 Criteria for Laboratory Test Values with Potential Clinical Relevance
- CT-10.2.1 Listing of Laboratory Test Values with Potential Clinical Relevance by Subject (Safety Sample)
- CT-10.2.2 Listing of Laboratory Test Values with Potential Clinical Relevance by Test (Safety Sample)
- CT-10.2.3 Incidence of Laboratory Test Values with Potential Clinical Relevance (Safety Sample)
- CT-10.3.1 Mean Change from Baseline in Clinical Laboratory Test Results - Serum Chemistry (Safety Sample)
- CT-10.3.2 Mean Change from Baseline in Clinical Laboratory Test Results - Hematology (Safety Sample)
- CT-10.3.3 Mean Change from Baseline in Clinical Laboratory Test Results - Urinalysis (Safety Sample)
- CT-10.3.4 Mean Change from Baseline in Clinical Laboratory Test Results - Prolactin, by Sex (Safety Sample)
- CT-10.3.5 Mean Change from Baseline in Clinical Laboratory Test Results - Other Tests (Safety Sample)
- CT-10.4.1 Incidence of Laboratory Test Values with Potential Clinical Relevance - Prolactin (Safety Sample)
- CT-10.4.2 Listing of Laboratory Test Values with Potential Clinical Relevance - Prolactin (Safety Sample)
- CT-10.5.1.1 Incidence of Treatment-Emergent Significant Change in Lipids (Safety Sample)
- CT-10.5.1.2 Listing of Treatment-Emergent Significant Change in Lipids (Safety Sample)
- CT-10.5.2.1 Incidence of Treatment-Emergent Significant Change in Glucose (Safety Sample)
- CT-10.5.2.2 Listing of Treatment-Emergent Significant Change in Glucose (Safety Sample)
- CT-10.5.3.1 Incidence of Treatment-Emergent Metabolic Syndrome (Safety Sample)

- CT-10.5.3.2 Listing of Treatment-Emergent Metabolic Syndrome (Safety Sample)
- CT-10.6 Incidence of Potentially Liver Injury Related Laboratory Test Abnormalities (Safety Sample)
- CT-10.7 Listing of Potentially Liver Injury Related Laboratory Test Abnormalities (Safety Sample)
- CT-11.1 Criteria for Potentially Clinically Relevant Abnormalities in Vital Signs
 - CT-11.2.1 Listing of Potentially Clinically Relevant Abnormalities in Vital Signs (Safety Sample)

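### Most SAP laboratory flags, prolactin among them, ignore baseline, so the incidence tables mix abnormalities carried into the trial with new ones

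*SAP*

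**What the plan says.** - **What is counted.** SAP 9.2 says: "Potentially clinically relevant laboratory measurement test results in the open-label treatment period will be identified for the Safety Sample and will be summarized" by parent-study group. The limits are in SAP Appendix 2. Neither place conditions on the baseline value, except that hematocrit needs a threshold plus a fall of at least 3 "percentage points from Baseline", and urine protein, glucose and casts are defined as a rise of at least 2 units.
- **Where it is tabulated.** CT-10.2.3 covers all tests. CT-10.4.1 is "Incidence of Laboratory Test Values with Potential Clinical Relevance - Prolactin (Safety Sample"), with a criterion of any value above ULN. The other planned prolactin summary is CT-10.3.4, "Mean Change from Baseline in Clinical Laboratory Test Results - Prolactin, by Sex (Safety Sample").
- **Baseline.** SAP 7.1: "Baseline is defined as the last available measurement prior to the first dose of open-label IMP in the open-label treatment phase". For ordinary rollover subjects, SAP 3.1 says "The assessments from the last scheduled treatment visit of the previous double-blind trial will serve as the baseline measures for this trial". Delayed-entry subjects have their own baseline visit.
- **Entry.** Protocol 5.2.2, criterion 4, says "subjects with the following laboratory test and ECG results at screening must be excluded from the trial" and lists fixed limits. Prolactin is not on the list.
- **Rules elsewhere in the SAP.** For most vital-sign and ECG rows, footnote a of Appendices 1 and 3 also requires a change from the "baseline value of at least the magnitude shown in the" adjoining column. SAP 9.2.2 (lipids, fasting glucose), 9.4 (new-onset QTc) and 9.6 (emergent suicidal ideation and behavior) define emergence against baseline.

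**The concern.** A table labelled incidence is normally read as what arose on treatment. Under a bare threshold, a subject with the same abnormal value at baseline and at Week 12 is counted exactly like a subject who became abnormal. Laboratory change, with prolactin named, is a secondary safety endpoint (Protocol Table 3-1), and the prolactin flag is any excess over ULN.

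Two conclusions are at stake. The first is how many subjects newly became abnormal on open-label brexpiprazole. The second is whether parent-study groups differ: they reach open-label baseline after different double-blind treatments, so their baseline shares of abnormal values may differ.

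**Working it through.** **Step 1. Count the criteria (SAP Appendix 2, Protocol 5.2.2, SAP 9.2.2).**

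| Set | Parameters | Number |
|---|---|---|
| All in Appendix 2 | | 29 |
| With a change condition | hematocrit; urine protein, glucose, casts | 4 |
| Bare thresholds | 29 − 4 | 25 |
| Barred at entry at or inside the flag limit | AST, ALT (> 2 × ULN against a flag of ≥ 3 × ULN); creatinine (≥ 2 mg/dL in both) | 3 |
| Partly barred | platelets (low side only); CPK (unless the medical monitor approves) | 2 |
| Separate baseline-referenced incidence table | glucose, LDL, HDL, triglycerides | 4 |
| Neither safeguard | 25 − 3 − 2 − 4 | 16 |

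The 16 are prolactin, ALP, LDH, BUN, uric acid, bilirubin, hemoglobin, WBC, eosinophils, neutrophil percentage, ANC, chloride, potassium, sodium, calcium and total cholesterol.

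Three qualifications apply:
- Chloride is not among the tests in Protocol Table 10.2-1. If it is not measured, the working number is 15.
- Bilirubin enters the liver-injury table of SAP 9.2.1, but only jointly with AST or ALT.
- The 9.2.2 limits do not always match Appendix 2. For example, fasting glucose is flagged at ≥ 100 mg/dL, but its baseline-category rows count shifts to ≥ 126 mg/dL.

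Two fixed entry limits are looser than the flags. Hemoglobin is excluded at ≤ 9 g/dL but flagged at ≤ 11.5 (men) and ≤ 9.5 (women). ANC is excluded at ≤ 1000/mm³ but flagged at ≤ 1500.

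**Step 2. What the table estimates.** Laboratory tests are scheduled only at baseline and Week 12/ET (Protocol Table 1.3-1); unscheduled tests are allowed. Let p be the share meeting the criterion at baseline, s the share of those still meeting it on treatment, and n the new-onset rate in the rest.

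Reported rate = p × s + (1 − p) × n = n + p × (s − n)

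The reported rate exceeds n whenever s exceeds n. The plan states no rate or sample size, so there is no figure to reproduce, and p, s and n are all assumptions.

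| p | s | Reported, n = 5% | Ratio to n | Share carried in | Reported, n = 10% | Ratio to n |
|---|---|---|---|---|---|---|
| 1% | 50% | 5.45% | 1.09 | 9% | 10.4% | 1.04 |
| 5% | 50% | 7.25% | 1.45 | 34% | 12.0% | 1.2 |
| 10% | 80% | 12.5% | 2.5 | 64% | 17.0% | 1.7 |
| 20% | 80% | 20.0% | 4.0 | 80% | 24.0% | 2.4 |
| 30% | 80% | 27.5% | 5.5 | 87% | 31.0% | 3.1 |

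The share carried in is p × s divided by the reported rate, for n = 5%.

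**Step 3. Group comparison.** With the same s and n in both groups, the reported gap is (p₁ − p₀) × (s − n).
- p = 20% against 5%, s = 80%, n = 5%: 0.15 × 0.75 = 11.25 points (20.0% against 8.75%).
- p = 10% against 5%, s = 50%, n = 5%: 0.05 × 0.45 = 2.25 points (9.5% against 7.25%).

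New onset is equal in both cases, so the whole gap comes from baseline.

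**The case against.** The case for leaving the plan alone has five parts.

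- **The table does what was asked.** Protocol 9.4.2.2 calls for the incidence of potentially clinically relevant values, whereas 9.4.2.4 speaks of changes for ECG. The titles of CT-10.2.3 and CT-12.2.2 keep that distinction. This stands: the SAP does not depart from the protocol. The point concerns what the table can show.
- **The endpoint is already referred to baseline.** Mean change is planned, by sex for prolactin. This stands, but a mean does not say how many subjects became abnormal.
- **Important changes become adverse events.** Protocol 8.8.1 makes a clinically significant laboratory value an AE. That route depends on investigator judgment and does not give new-onset counts at the Appendix 2 limits.
- **Entry screening limits carry-in.** Criterion 4 also excludes any abnormal result unless it is judged not medically significant, and Protocol 8.7.1 requires the medical monitor's permission to enroll a subject with a clinically significant one. This narrows carry-in to values judged unimportant or accepted on review. A prolactin value just above ULN could be one of these.
- **A new-onset rule can hide signals.** Elevations that arose during double-blind brexpiprazole would drop out of the count, as would a subject moving from just above ULN to several times ULN. This is the strongest objection. It is why the all-subject count should stay.

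A reader might also infer that the vital-sign and ECG tables always require change, so that the laboratory table breaks a uniform rule. They do not: orthostatic hypotension disregards baseline status and the QTcF row of Appendix 3 gives no change threshold, although QTc has new-onset categories in SAP 9.4.

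**Conclusion.** The point holds for most laboratory criteria, not all: 25 of 29 have no baseline condition, and 16, including prolactin, also lack both an entry exclusion at the flag limit and a baseline-referenced laboratory incidence table. For these, CT-10.2.3 and CT-10.4.1 cannot separate carried-in from new abnormalities, and a difference between parent-study groups may reflect baseline alone.

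The size cannot be computed from the documents. It ranges from almost nothing when few subjects are abnormal at baseline (5.45% against 5% at p = 1%, s = 50%) to several-fold when p is large and n small.

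Three stronger readings are tempting but unsupported:
- **Entry limits are generally looser than the flags.** They are stricter for AST and ALT and equal for creatinine and low platelets.
- **Incidence is overstated about tenfold.** p = 40%, s = 80%, n = 3% gives 33.8%, or 11.3 times n, but that pairs a high assumed p with a low assumed n, and neither comes from the documents.
- **Prolactin rises would otherwise go unseen.** Mean change, the listing CT-10.4.2 and AE reporting remain.

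**What to change.** In SAP 9.2, keep the all-subject count of flagged values and add to CT-10.2.3 and CT-10.4.1:

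1. New-onset incidence among subjects who did not meet the criterion at baseline and have a post-baseline value, with those subjects as the denominator.
2. A separate row or shift table for subjects already meeting the criterion at baseline, showing persistence and worsening.

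Present both by sex for prolactin. Leave listings CT-10.2.1, CT-10.2.2 and CT-10.4.2 unrestricted, with the baseline value displayed.

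This needs SAP wording and programming on data already collected. The cost is a few more table rows and smaller, less precise denominators for the new-onset rates.

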9.2.1 Drug Induced Liver Injury (DILI)

Total bilirubin level should be checked for any subject with increased ALT or AST levels \geq three times the upper normal limits (ULN) or baseline.

- Reporting all DILI as SAE to the FDA based on Hy's Law:
 - AST or ALT $\geq 3 \times$ ULN or baseline and
 - T_Bili $\geq 2 \times$ ULN or baseline

A separate incidence table will be provided for DILI cases, and the corresponding listing will be provided for Safety Sample during the open-label treatment period.

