1.3 Schedule of Assessments

Assessment	Visit								Post-treatment Follow-up ^f	
	Treatment Period									
	Screening/ Baseline ^{a,b}	Week 1 ^{c,d}	Week 2 ^c	Week 4 ^c	Week 6 ^{c,d}	Week 8 ^c	Week 10 ^{c,d}	Week 12 or ET ^{c,e}		
		± 3 days							21 ± 3 days	
ENTRANCE CRITERIA										
Informed consent ^g	X									
Inclusion and exclusion criteria ^g	X									
Confirmation of eligibility ^g	X									
Medical history ^g	X									
Psychiatric history, including BPD history ^g	X									
CCI										
SAFETY										
Physical examination ⁱ	X							X		
Vital signs ^j	X		X	X		X		X		

Table 1.3-1 Schedule of Assessments

Assessment	Visit Treatment Period								Post-treatment Follow-up ^f
	Screening/ Baseline ^{a,b}	Week 1 ^{c,d}	Week 2 ^c	Week 4 ^c	Week 6 ^{c,d}	Week 8 ^c	Week 10 ^{c,d}	Week 12 or ET ^{c,e}	
		± 3 days							
Clinical laboratory tests (hematology [including HbA1c], serum chemistry [including prolactin], urinalysis)	X ^k							X ^l	
ECG ^m	X							X	
Urine pregnancy test (FOCBP only) ⁿ	X			X		X		X	
Urine drug screen and blood alcohol test ^o	X							X	
C-SSRS ^p	X		X	X		X		X	
EPS scales (SAS, AIMS, BARS)	X			X		X		X	
Adverse events ^q	X	X	X	X	X	X	X	X	X
Concomitant therapy ^r	X	X	X	X	X	X	X	X	X
OTHER PROCEDURES									
IMP dispensing ^g	X		X	X		X			
IMP accountability			X	X		X		X	
Dose adjustment ^s			X	X		X		X	
Schedule optional telephone contact/other communication ^t			X	X	X	X	X		

FOCBP = female of childbearing potential.

^aScreening for Trial 331-201-00195 occurs on the same day as baseline but prior to any procedures specific to the open-label trial. Informed consent for Trial 331-201-00195 should be signed at the start of the last double-blind treatment visit. The screening/baseline for Trial 331-201-00195 will be the same day as the last visit of the previous double-blind trial.

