8.8.6 Potential Serious Hepatotoxicity

For a subject who experiences an elevation in AST or ALT that is ≥ 3 times the ULN, a total bilirubin level should also be evaluated. If the total bilirubin is ≥ 2 times the ULN, complete an IRE form with all values listed and also report as an AE in eSource.

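### The SAP's liver-injury case rule uses ULN or baseline with no floor at ULN, so a subject with all-normal liver tests can, rarely, be counted as a case

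*SAP*

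**What the plan says.** SAP section 9.2.1 gives two criteria, both of which must be met, and ties them to Hy's Law: "AST or ALT $\geq 3 \times$ ULN or baseline and" "T_Bili $\geq 2 \times$ ULN or baseline". It then says that "A separate incidence table will be provided for DILI cases", with a matching subject listing for the Safety Sample. The only liver-injury outputs in SAP section 12 are CT-10.6, "Incidence of Potentially Liver Injury Related Laboratory Test Abnormalities (Safety Sample"), and the companion listing CT-10.7.

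Four other places bear on the rule:

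- **SAP 7.1** defines baseline as the last value before the first open-label dose, so it can lie anywhere in the normal range.
- **Protocol 5.2.2** excludes "Alanine aminotransferase (ALT) $> 2 \times$ ULN", with the same cap for AST. Baselines between 1 and 2 × ULN are therefore admissible.
- **Protocol 8.8.6**, the site criterion, uses ULN only. AST or ALT at 3 × ULN or more prompts a bilirubin check, and if bilirubin is at least "2 times the ULN, complete an IRE form with all values listed". The AST and ALT rows of SAP Appendix 2 are also ULN-only.
- **SAP section 1** gives the SAP precedence where its analyses differ from the protocol's.

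**The concern.** The words added after ULN can be applied in two ways.

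- **Literal reading.** A value qualifies if it reaches the multiple of ULN or the multiple of the subject's own baseline. A subject with low-normal baseline values can then be a case without any value leaving the normal range.
- **Substitution reading.** Baseline replaces ULN as the reference when baseline is raised. No all-normal subject then qualifies, but some subjects who meet the site criterion in Protocol 8.8.6 drop out of the table.

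The SAP does not say which applies, so two programmers could derive different cases from the same data. Under either reading the table may not match the immediately reportable event forms that sites file. The trial's stated objective is safety, and a count labelled as liver injury under Hy's Law is one that readers will take seriously even at one or two subjects.

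**Working it through.** The plan states no figure to reproduce. The check has an exact part and an illustrative part.

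**Exact thresholds.** Let b = baseline ÷ ULN.

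- Literal reading: ALT or AST threshold = min(3, 3b) × ULN; bilirubin threshold = min(2, 2b) × ULN.
- Substitution reading: ALT or AST threshold = max(3, 3b) × ULN.

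| b | ALT/AST, literal | Bilirubin, literal | ALT/AST, substitution |
|---|---|---|---|
| 0.25 | 0.75 | 0.5 | 3 |
| 1/3 | 1.0 | 0.67 | 3 |
| 0.5 | 1.5 | 1.0 | 3 |
| 1 | 3 | 2 | 3 |
| 2 | 3 | 2 | 6 |

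Three things follow.

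1. Under the literal reading the baseline alternative has no effect once b ≥ 1. It never adjusts for a raised baseline; it only loosens the rule for subjects who start below ULN.
2. An all-normal case needs baseline ALT or AST at or below ULN/3 and baseline bilirubin at or below ULN/2. For example, with assumed ULNs of 40 U/L and 1.2 mg/dL, take ALT rising from 10 to 30 and bilirubin from 0.3 to 0.6. Since 30 = 3 × 10 and 0.6 = 2 × 0.3, the subject is counted. The ULN-only limits would be 3 × 40 = 120 and 2 × 1.2 = 2.4, and neither is reached.
3. Under the substitution reading, a subject entering at ALT 2 × ULN and rising to 4 × ULN, with bilirubin at or above 2 × ULN, meets Protocol 8.8.6 but misses the table threshold of 6 × ULN.

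**How often (every rate input is assumed; none comes from the documents).** The simulation is log-normal with no drug effect and about 8,000,000 subjects per setting. Medians are 0.5 × ULN for ALT and AST and 0.45 × ULN for bilirubin. The between-person log SD is 0.4, the ALT–AST correlation is 0.7, and bilirubin is independent. From the documents it takes only the entry cap of 2 × ULN on ALT and AST and one post-baseline draw, because Protocol 1.3 schedules chemistry only at baseline and Week 12/ET.

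| Per-draw log SD (ALT and AST / bilirubin) | Literal rule, all flags | Of which all-normal | ULN-only rule |
|---|---|---|---|
| 0.2 / 0.2 | 0.0001% | below 0.0001% | 0 |
| 0.3 / 0.3 | 0.047% | 0.018% | below 0.0001% |
| 0.4 / 0.35 | 0.37% | 0.13% | 0.0003% |

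The all-normal figure in the first row rests on 3 simulated subjects and gives an order of magnitude only. At the widest SDs, using ALT alone gives an all-normal rate of 0.09%. Medians of 0.3 × ULN for all three analytes give 0.27%; medians of 0.6 (ALT, AST) and 0.55 (bilirubin) give 0.07%. Adding a requirement that both on-treatment values exceed ULN cuts all flags at the widest SDs from 0.37% to 0.045%.

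**The case against.** The strongest reply is that the literal reading was probably not meant. Section 9.2.1 speaks of increased transaminases, invokes Hy's Law, and feeds outputs whose titles refer to abnormalities. That is fair as to intent. But the word appears only in the sentence about checking bilirubin, not in the case criteria, and a threefold rise within the normal range is also an increase. The likelier intent is not written down, and the substitution reading has its own conflict with the site criterion.

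The second reply is size, and it stands. At the middle setting one expected all-normal subject needs about 1 ÷ 0.00018 ≈ 5,600 subjects; at the widest, 1 ÷ 0.0013 ≈ 770; at the lowest medians, 1 ÷ 0.0027 ≈ 370. The documents give no sample size to set against these figures. Unscheduled draws, which Protocol 8.7.1 allows, would raise the rates somewhat. No test or stopping rule uses the count, and the listing would reveal an all-normal subject, though the incidence count would still include that subject. The simulation contains no true liver injury, so its near-zero ULN-only rate does not show how spurious cases would compare with real ones.

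Third, a table may properly cast a wider net than a site reporting trigger, and Appendix 2 serves a different output. Both are true, but a wider net should not carry the Hy's Law label without saying how it differs.

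Last, a ULN-only row might discard a deliberate adjustment for raised baselines. A separate baseline-relative row keeps room for that aim.

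**Conclusion.** The concern holds. As written, the case definition lacks a floor at ULN and leaves the role of baseline open. The literal rule can count subjects whose values are all normal, and the alternative can omit subjects whom sites must report. The threshold results are exact. The rates are illustrative: all-normal counts run from below 0.0001% to about 0.13% of subjects at the central medians, and up to 0.27% at the lowest, resting wholly on assumed medians and variability. Such cases should be rare, and the adverse-event primary analysis is unaffected. The point is worth correcting because a stated rule can give a wrong safety count and can be programmed in more than one way.

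**What to change.** For CT-10.6 and CT-10.7 only, define the Hy's Law row as AST or ALT at least 3 × ULN together with total bilirubin at least 2 × ULN, matching the multiples in Protocol 8.8.6. If a baseline-relative summary is wanted, give it its own row under a different name, require the on-treatment values to exceed ULN as well, and state exactly how baseline enters. This follows the SAP's own practice: Appendix 1 (footnote a) and the hematocrit criterion in Appendix 2 require a limit and a change together, while section 9.2.2 gives pure changes from baseline their own rows.

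Separately, the sponsor must reconcile the bilirubin-check trigger in SAP 9.2.1 with Protocol 8.8.6. It must also reconcile the SAP's description of these cases as SAEs with Protocol 8.8.1, 8.8.3 and 8.8.6, which list potential serious hepatotoxicity as its own class of immediately reportable event. No clinical or reporting rule is proposed here.

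The tabulation change costs one SAP sentence and the derivation of two outputs. No new data are needed.
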